11. Unable to receive, or unlikely to absorb, study drug (e.g. bowel obstruction, ischemia, or infarction; short gut syndrome)
12. Body mass index $>$ 40
13. Patient not expected to survive $>$ 4 days
14. Pregnancy (based on urine or blood test results based on standard practice in the subject's ICU) or lactation
15. Allergy to lorcaserin or lorcaserin taken in the prior 7 days
16. Enrolled in another interventional drug or physical rehabilitation trial
17. Physician declines for patient to be enrolled
18. Patient or proxy declines consent
19. Unable to reach proxy for consent
20. Non-English speaking

6) Drugs/ Substances/ Devices

6-a) The rationale for choosing the drug and dose or for choosing the device to be used.

It is known that activation of serotonin receptors (5-HT_{2C}) in the spinal cord increases persistent inward sodium current to allow motor neurons to fire repetitively, and lorcaserin, as a selective 5-HT_{2C} agonist was used successfully in rat models (see Background, section 3-d)

The lorcaserin dose that normalizes motor neuron firing in rats is 3 mg/kg. The human dose for weight loss is 10 mg PO twice daily, but doses up to 60 mg were tolerated in clinical trials. Based on rat-to-human allometric scaling of both pharmacokinetic parameters and 5-HT_{2C} receptor sensitivity (EC₅₀), the 3 mg/kg dose in a rat is

Date: 1 August 2016

Principal Investigator: [name] PhD

Application Number: IRB00072940

0.26 mg/kg or 18 mg in a 70 kg adult. Based on doses of lorcaserin that were given to patients prior to FDA approval and rat to human allometric scaling, it appears that treatment of patients with effective doses of lorcaserin is feasible (See Background, section 3-e)

6-b) Justification and safety information if FDA approved drugs will be administered for non-FDA approved indications or if doses or routes of administration or participant populations are changed.

See attached IND Exemption document

6-c) Justification and safety information if non-FDA approved drugs without an IND will be administered.

Not Applicable

7) Study Statistics

7-a) Primary outcome variable.

The primary analysis will compare the mean change in hand grip strength from baseline to post-drug testing across the 30 mg intervention dose vs. control group using a two-sample t-test.

7-b) Secondary outcome variables.

Secondary analyses will include the following:

- 1) replication of the primary analysis for the 10 mg intervention dose vs. control group,

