- 2) replication of the primary analysis excluding any patients with neuropathy based on nerve conduction studies (29) within the intervention group,
- 3) comparison of the change from baseline to post-drug testing across the 10 mg versus 30 mg conditions using a paired t-test
- 4) a PK-PD analysis for all concentration-strength measures for all observations (across the 4 days) using a traditional Emax model pooling all subjects and all time points.

7-c) Statistical plan including sample size justification and interim data analysis.

The sample size (N=10 for lorcaserin and N=5 for placebo) is a convenience sample to establish preliminary data for a potential larger future study. With $\alpha = 0.05$, power = 80%, and a mean (standard deviation) baseline value of 9 (9) kg for the primary outcome of grip strength, under a 30 mg dose of lorcaserin we could detect a difference of >9 kg for the change in strength from baseline to post-drug testing (on the same day) for the intervention group versus no change for the placebo group. This difference represents a 100% increase in strength versus a 400% increase detected with an equivalent dose in the rat model. This calculation assumes that the baseline and post-drug testing measures would be highly correlated ($r = 0.8$). Under a worst case scenario (i.e., no correlation between baseline and post-drug testing), we could detect at least a 220% increase in strength which is adequate given the large increase expected based on rat models.

7-d) Early stopping rules

There are no early stopping rules for this pilot trial.

8) Risks

8-a). Medical risks, listing all procedures, their major and minor risks and expected frequency.

1) Side effects of Drug / Placebo:

Participants will be closely monitored for any side effects related to administration of the study drug or placebo.

The placebo has no known side effects.

Date: 1 August 2016

Principal Investigator: [name] PhD

Application Number: IRB00072940

The study drug, lorcaserin, has been extensively studied, has an excellent safety profile and is FDA approved for chronic use for purposes of weight loss(19). The major potential side-effects are listed below. A full list of side effects is available in Appendix C, the FDA prescribing information.

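### Does the primary t-test on change in grip strength need to be replaced by an analysis adjusted for pre-dose grip (ANCOVA)?

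*Combined protocol and SAP*

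**What the plan says.** Section 7-a makes the primary analysis a comparison of the "mean change in hand grip strength from baseline to post-drug testing across the 30 mg intervention dose vs. control group using a two-sample t-test". Section 7-c specifies that the change is measured within one day, so for the 30 mg dose it runs from Day 3 pre-dose to Day 3 post-dose grip. Section 7-b carries the method over to a "replication of the primary analysis for the 10 mg intervention dose vs. control group". No covariate-adjusted model appears in section 7.

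Section 7-c describes the 10 lorcaserin and 5 placebo patients as a "convenience sample to establish preliminary data for a potential larger future study". It takes "a mean (standard deviation) baseline value of 9 (9) kg for the primary outcome of grip strength" and derives a detectable difference above 9 kg "for the intervention group versus no change for the placebo group". On correlation it says: "This calculation assumes that the baseline and post-drug testing measures would be highly correlated", with r = 0.8. It then gives a bound: "Under a worst case scenario (i.e., no correlation between baseline and post-drug testing), we could detect at least a 220% increase in strength", and calls that adequate.

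The footnotes to Table 3 place the pre-dose measurement within 4 hours of dosing and the post-dose measurement 2 to 6 hours after it.

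**The concern.** A change score assumes that each kilogram of pre-dose grip carries through in full to post-dose grip. With equal SDs the true slope equals the correlation r, so the subtraction over-corrects whenever r is well below 1. ANCOVA estimates the slope from data the trial already collects and costs one degree of freedom.

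The plan gives no source for r = 0.8 and itself considers r = 0. If r were low, the t-test on change would give a wider interval than necessary, in a trial whose purpose is to supply estimates for a larger one. Prespecifying ANCOVA would then look like a free improvement that the plan overlooked.

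**Working it through.** **Inputs.** From section 7-c: 10 and 5 patients, alpha 0.05, power 80%, baseline mean and SD both 9 kg, r = 0.8 or 0. Assumed because the plan does not state them: a two-sided test, normal data, and post-dose SD of 9 kg in both arms. The values of r other than 0.8 and 0 are also assumptions.

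**Reproducing the plan's figures.** SD of change = 9·√(2 − 2r); SE = SD·√(1/10 + 1/5) = SD·√0.3.

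- r = 0.8: SD = 5.692, SE = 3.118. The normal multiplier 1.960 + 0.842 = 2.802 gives 8.73 kg, or 97% of 9 kg.
- r = 0: SD = 12.728, SE = 6.971. The same multiplier gives 19.53 kg, or 217%.

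These match the stated 9 kg and 220% closely. The exact noncentral t on 13 df has a multiplier of 3.031 and gives 9.45 kg (105%) and 21.13 kg (235%).

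**t-test on change against ANCOVA.** For ANCOVA, residual SD = 9·√(1 − r²). Its variance is inflated on average by (N − 3)/(N − 4) = 12/11 for chance imbalance in pre-dose grip. With 12 df the multiplier is 3.053. Worked at r = 0.8: 5.40·√(0.3·12/11) = 3.089, and 3.053·3.089 = 9.43 kg.

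| r | t-test on change (kg) | ANCOVA (kg) | ANCOVA relative to t-test |
|---|---|---|---|
| 0 | 21.13 | 15.72 | 26% lower |
| 0.5 | 14.94 | 13.61 | 9% lower |
| 0.7 | 11.57 | 11.22 | 3% lower |
| 0.8 | 9.45 | 9.43 | no difference |
| 0.85 | 8.18 | 8.28 | 1.2% higher |
| 0.9 | 6.68 | 6.85 | 2.5% higher |
| 0.95 | 4.73 | 4.91 | 3.9% higher |

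The methods cross at about r = 0.81. In simulation under no effect, with normal data and equal variances, both reject at 5% for r = 0, 0.5 and 0.8. The planned test is therefore valid under its own assumptions.

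**Carryover from Day 1.** The Day 3 pre-dose value is taken after randomisation and after the 10 mg dose. Section 3-f expects strength to be back at baseline after 48 hours, which is an assumption. Suppose an effect c persists and 30 mg adds nothing. Both Day 3 measurements in the treated arm rise by c. Same-day change then averages c − c = 0, and ANCOVA averages c·(1 − slope), with slope = r here. For an assumed c = 3 kg:

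- r = 0.8: 3·0.2 = 0.6 kg
- r = 0.5: 3·0.5 = 1.5 kg
- r = 0: 3·1 = 3.0 kg

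Simulation confirms these averages. ANCOVA falsely rejects in about 5.4%, 6.1% and 8.3% of trials, while the t-test on change stays at 5%. The bias is largest exactly where ANCOVA's precision gain is largest.

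**Effect proportional to baseline.** Section 7-c says of its 9 kg: "This difference represents a 100% increase in strength". If each treated patient doubles, treated post-dose SD becomes 18 kg. At r = 0.8:

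- Variance of change is 18² + 9² − 2·0.8·18·9 = 145.8 on lorcaserin and 9²·0.4 = 32.4 on placebo.
- SD of the difference in mean change is √(145.8/10 + 32.4/5) = √21.06 = 4.59 kg.
- ANCOVA's SD in simulation is 5.08 kg, 11% larger.
- Mean 95% CI half-width is the same (12.18 against 12.17 kg), and power at 9 kg is about 28% against 29%.

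The reason is the slope. The within-arm slopes are 1.6 and 0.8, and ANCOVA pools them by degrees of freedom: (9·1.6 + 4·0.8)/13 = 1.35. The slope that minimises the variance weights the arms by 1/n: (1.6/10 + 0.8/5)/0.3 = 1.07. The fixed slope of 1 lies closer to that optimum.

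**The case for a change.** The best case for ANCOVA is this. The value r = 0.8 has no cited source. With normal data and equal variances, ANCOVA is at least as precise over the plan's whole range from 0 to 0.8, and above that it loses no more than about 5%. It needs no new data, and fixing the model in advance avoids a later choice in a very small trial.

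Skewness adds to that case. A normal distribution with mean and SD both 9 kg puts 16% of patients below zero, so grip is probably skewed. Under assumed lognormal or exponential grip with r = 0.8, and no effect or a constant gain, ANCOVA's estimate has a 15% or 6% smaller SD.

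That arithmetic stands, and a statistician who preferred ANCOVA would not be wrong. It does not make the present choice a fault:

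- The large gain requires r near 0, which the plan treats as its worst case and already accepts. Nothing in the documents points to low correlation between two measurements taken within hours of each other.
- Under the same skewed distributions, if lorcaserin doubles grip, ANCOVA averages 8.2 or 8.3 kg against a true 9.0 kg. The mean change stays unbiased.
- The two methods do not depend equally on washout. In fairness, an 11-hour half-life leaves 0.5^(48/11) = 4.9% of the dose at 48 hours, so carryover may be small. Only the change score is protected if it is not.

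Unequal variances do not separate the methods either. If placebo post-dose SD alone doubles (assumed, r = 0.8), both reject about 12% of the time under equal means.

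**Conclusion.** The concern does not hold. The two-sample t-test on same-day change is valid under its usual assumptions, already uses pre-dose grip by subtraction, and answers the question that section 7-a asks. At the plan's r = 0.8 with normal data and equal variances, switching to ANCOVA moves the detectable difference by 0.02 kg.

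Elsewhere the balance goes both ways. ANCOVA gains 9% at r = 0.5 and 26% at r = 0. It loses 1% to 5% above r = 0.81, and about 11% in estimator SD if treated patients double their grip at r = 0.8. It also takes on a carryover bias of (1 − slope) times any persisting 10 mg effect, which the change score avoids.

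These sizes rest on a two-sided 0.05 test, 10 vs 5 patients, and the assumed distributions, SDs and 3 kg carryover stated above. In a convenience-sample pilot the choice is one on which competent statisticians may differ. It is not a defect in the plan.

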3-a) Severe Muscle Weakness in Critical Illness is a Frequent, Serious and Costly Health Problem

[figure not shown]
One of the most devastating complications of critical illness is the poorly-understood, rapid and persistent severe weakness of skeletal muscles. In the United States, more than 750,000 people per year have sepsis with 380,000 requiring an intensive care unit (ICU) stay and mechanical ventilation(1). Studies suggest that from 1/3 to 1/2 of patients who require prolonged mechanical ventilation develop global, persistent weakness(2;3). From these data we estimate that in the U.S., 100,000 to 150,000 patients per year develop profound muscle weakness as a result of sepsis-associated critical illness. Development of weakness has an important economic impact, with a 4-fold increase in average hospital cost per patient(4). In addition, weakness results in important long-term impairments in physical functioning, quality of life and delayed return to work(5-7).

3-b) Incomplete understanding and ineffective treatment

Both a myopathy ("critical illness myopathy" - due to muscle atrophy and loss of myosin), and a neuropathy ("critical illness polyneuropathy" - due to death of axons) contribute to weakness(8;9). However, as reported in a recent study in a rat model(10), neither myopathy nor neuropathy fully account for weakness. A lack of understanding of the mechanisms causing weakness after critical illness has meant that the main therapies available are non-specific interventions, applied in hopes of promoting long-term recovery of neuromuscular function. These therapies include tight glycemic control (11) and physical therapy during critical illness(12;13), but these therapies have sub-optimal effect in patients with severe weakness.

3-c) Our newly published studies identify a novel potential mechanism for central nervous system (CNS) dysfunction in sepsis

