On Day 4, the intervention and control group participants will not receive any lorcaserin/placebo, but will undergo assessments (identical to Day 2).

4-a-6) Measurements

Participants will be monitored to ensure safety of lorcaserin/placebo administration. This monitoring will include a daily review of interim history (via chart review), medications, and laboratory values (details below), as well as assessment for changes in mental status and monitoring for serotonin syndrome (see table 3).

We also will obtain a battery of outcome measures to test the efficacy in improving muscle strength and assess the safety of lorcaserin, as described in tables 3.

All monitoring will be done by assessors blinded to group allocation.

Table 3: Safety and Efficacy Measures (numbers indicate the number of times within each study day that each measurement is performed)

Measurement	Number of assessments			
	Day 1*	Day 2†	Day 3***‡	Day 4†
Safety Measures				
Chart Review	1	1	1	1
Laboratory Tests (details below)	1	1	1	1
EKG	2	1	1	1
RASS sedation score	2***	1	2***	1
CAM-ICU delirium screen	2***	1	2***	1
Neuro Psychiatric Screen	2	1	1	1
Hunter Serotonin Toxicity Criteria	1	1	1	1

Efficacy Measures				
Handgrip Strength (Primary Outcome)	2***	1	2***	1
Arm & leg strength (MMT using MRC Scale)	2***	1	2***	1
Quadriceps Strength using handheld dynamometry	2***	1	2***	1
Lorcaserin serum drug levels [‡]	1	1	1	1
Electromyography & Nerve Conduction Study	once only to assess for any peripheral neuromyopathy****			

MMT: Manual muscle strength testing; MRC: Medical Research Council; HHD: Hand-Held Dynamometry; EKG: Electrocardiogram; RASS: Richmond Agitation Sedation Scale; NPI-C: Neuropsychiatric Inventory - Clinician Rating Scale; CAM-ICU: Confusion Assessment Method for the ICU; Hunter Criteria: will be used to evaluate patients for serotonin syndrome (24)

* 10 mg of lorcaserin or placebo administered

** 30 mg of lorcaserin or placebo administered

*** measures are performed as close to the time as drug or placebo administration as possible (within 4 hours) and as soon as possible (between 2 - 6 hours) after drug or placebo administration, on Days 1 and 3 only

**** EMG & NCS will be performed at any time point after the patient is randomized into study, and will be used to help interpret the results of strength tests

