4-a-6.11) Serum Drug Levels: Daily blood samples will be collected to determine lorcaserin serum levels by a LC-MS/MS assay and pharmacokinetics. The serum drug samples will be collected and run in at least 2 batches, with the first batch run on specimens after randomization of at least the first 3 patients to lorcaserin (will be done without unblinding the research team regarding the study ID of these subjects). The peak plasma concentration after oral dosing is 1.5 to 2 hours. However, feeding can increase the peak plasma time by 1 hour. Thus, peak concentration samples will be collected at 2hours \pm 15 minutes for NPO patients and at 3 hours \pm 15 minutes for fed patients. Lorcaserin has a plasma half-life of about 11 hours, and trough concentration samples will be collected at approximately two half-lives, or 24 hours \pm 30 minutes.

4-a-6.12) Electromyography (EMG) and Nerve Conduction Studies (NCS):

Nerve conduction will be assessed via the following screening nerve conduction studies in participants after enrolment, to detect potential peripheral neuropathy. NCS results will help us interpret the results of strength tests.

- Motor NCS of bilateral peroneal nerves
- Motor NCS of unilateral ulnar nerve. If ulnar neuropathy at the elbow is diagnosed (slowing of ulnar conduction velocity across the elbow to below 35 m/s or a drop in ulnar motor amplitude of >50% with stimulation above the elbow), Motor NCS of the ulnar nerve of the other extremity will be performed as well.

- Sensory NCS of unilateral ulnar and sural nerves

Motor unit recruitment rate will be assessed via the following EMG studies as well

- EMG of unilateral vastus lateralis muscle
- EMG of unilateral deltoid muscle

If EMG and NCS studies have already been done for clinical purposes, they will NOT be repeated for research purposes, and the pre-existing results will be used for research purposes.

4-b) Study duration and number of study visits required of research participants.

Each participant regardless of group, will be in the study for two 2-day blocks. The detailed timeline of events are detailed in Table 3.

4-c) Blinding, including justification for blinding or not blinding the trial, if applicable.

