 9. New-onset psychosis
 10. Onset of new symptoms of hallucinations or euphoria (as determined by NPI-C assessment as described above)
4. If the patient is given a sedative medication during this brief period between baseline and follow-up testing, with a change in mental status that prohibits the ability to perform muscle strength testing, no further testing or administration of lorcaserin/placebo will be done in that patient and a new patient would be recruited and consented in place of this patient.

4-g) Description of what happens to participants receiving therapy when study ends or if a participant's participation in the study ends prematurely.

Those who end their participation in this study prematurely will not be given any further lorcaserin/placebo doses. Similarly, lorcaserin/Placebo administration will cease upon the end of the study. Cessation of lorcaserin will not be harmful to the patient. There are no known adverse effects associated with withdrawal of lorcaserin and there is no need for tapering. Thus its absence or cessation will not directly cause any adverse outcomes. Patient care will continue without change after cessation of lorcaserin/placebo.

5) Inclusion/Exclusion Criteria

5-a) Inclusion Criteria:

1. Age \geq 18 years old
2. Sepsis [\geq 2 Systemic Inflammatory Response Syndrome (SIRS) Criteria AND known or suspected infection]
3. Muscle weakness [Medical Research Council sum score $<$ 48/60 or handgrip strength $<$ 11 kg in men and $<$ 7 kg in women]
4. Obey Commands [Score for DeJonghe Awakening Score of \geq 3/5]

5-b) Exclusion Criteria (based on medical record review and discussion with patient/surrogate)

1. Severe renal insufficiency [Creatinine Clearance $<$ 30 mL/min – or receiving dialysis]
2. Acute infectious or auto-immune hepatitis, acute liver failure, or a history of cirrhosis without liver transplant
3. History of psychosis
4. Bradycardia, or 2nd or 3rd degree AV block without pacemaker
5. History of valvular heart disease without valve replacement
6. History of priapism
7. Receiving drugs with serotonergic effects and/or CYP2D6 substrates which cannot be substituted stopped or titrated (as described in section 4d).
8. Receiving Sulfonylurea medication at the time of the study
9. Prior neuromuscular or central nervous system disease, including pre-existing neuropathy
10. Inability to perform study's muscle strength assessments based on patient's baseline status prior to hospital admission

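### Secondary analysis 2, as worded, removes neuropathy patients from the lorcaserin arm only, so it no longer compares like with like

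*Combined protocol and SAP*

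**What the plan says.** The primary analysis (section 7-a) compares mean change in grip strength "across the 30 mg intervention dose vs. control group using a two-sample t-test". Item 2 of section 7-b is a "replication of the primary analysis excluding any patients with neuropathy based on nerve conduction studies (29) within the intervention group". No other section extends this exclusion to placebo or gives a reason for treating the arms differently.

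Four other places bear on the point:

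- Section 4-a-6.12 plans the nerve studies without regard to arm: "Nerve conduction will be assessed via the following screening nerve conduction studies in participants after enrolment". A footnote to Table 3 adds that "EMG & NCS will be performed at any time point after the patient is randomized into study".
- Post-dose strength testing on dosing days is to be done "as soon as possible (between 2 - 6 hours) after drug or placebo administration" (Table 3 footnote), so the change analysed is over hours.
- The sample size text in section 7-c takes a gain "for the intervention group versus no change for the placebo group". It says nothing about change by neuropathy status.
- Exclusion criterion 9 in section 5-b removes "Prior neuromuscular or central nervous system disease, including pre-existing neuropathy", so item 2 concerns neuropathy first found in the study.

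**The concern.** Randomisation balances neuropathy between arms in expectation. Removing neuropathy patients from one arm undoes that balance by design. Any difference in item 2 could then come partly from the drug and partly from the unequal filter, and the analysis could not separate the two.

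Item 2 cannot be read as a within-arm analysis, because it repeats a two-arm test. At stake is whether it can be interpreted as the drug effect with neuropathy patients set aside, which could inform the larger study for which this pilot is meant to supply preliminary data. The primary result, the safety objective and the sample size are not affected.

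**Working it through.** **Inputs from section 7-c.** 10 lorcaserin and 5 placebo patients; baseline grip mean 9 kg, SD 9 kg; correlation of baseline and post-drug grip r = 0.8; α = 0.05 (two-sided assumed).

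**The plan's own figure.** SD of change = 9 × √(2 × (1 − 0.8)) = 5.69 kg. With 10 vs 5 and 80% power, the detectable difference is 8.73 kg by normal approximation and 9.45 kg by noncentral t. These lie either side of the stated 9 kg. At r = 0 the SD of change is 12.73 kg and the normal approximation gives 19.5 kg, or 217% of 9 kg, in line with the stated 220%. The inputs are therefore read correctly.

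**Bias of the one-arm exclusion.** Let p be the share with neuropathy, d the amount by which untreated change is lower in those patients, and m the untreated mean change in patients without neuropathy. With an inactive drug:

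- lorcaserin after exclusion: mean change m
- placebo, not filtered: (1 − p) × m + p × (m − d) = m − p × d
- difference: p × d

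Positive d favours lorcaserin, negative d favours placebo, and d = 0 gives no bias.

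**Size.** Neither p nor d is in the documents, so the ranges are assumptions. Each cell comes from 60,000 simulated trials (10 vs 5, SD of change 5.69 kg, no drug effect, pooled t-test) and shows the mean difference in kg, with two-sided type I error in brackets, for item 2 as written:

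| d (kg) | p = 0.1 | p = 0.2 | p = 1/3 | p = 0.5 |
|---|---|---|---|---|
| 0 | 0.00 (0.050) | -0.03 (0.050) | -0.01 (0.050) | -0.01 (0.050) |
| 1 | +0.09 (0.051) | +0.21 (0.049) | +0.32 (0.050) | +0.50 (0.052) |
| 3 | +0.29 (0.051) | +0.61 (0.054) | +0.99 (0.059) | +1.49 (0.065) |
| 5 | +0.49 (0.054) | +0.99 (0.061) | +1.66 (0.075) | +2.48 (0.090) |
| -3 | -0.32 (0.051) | -0.60 (0.054) | -0.99 (0.059) | -1.48 (0.064) |

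The standard error of the difference is 3.2 to 3.9 kg, so the largest bias is about 0.65 standard errors. A d of 3 to 5 kg is 33% to 56% of the 9 kg baseline mean (3/9 and 5/9) arising within hours, so those rows are upper-end cases.

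**Same exclusion in both arms.** The mean difference stays within 0.03 kg of zero and type I error between 0.048 and 0.052 in every cell.

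**The case against.** Three arguments on the other side carry weight.

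First, the harm needs a nonzero d, and nothing in the documents shows one. Section 3-b says that neuropathy contributes to weakness, but that concerns the level of strength, not its untreated change over hours. The planning assumption of no mean change on placebo would fit d = 0. This stands as a reason to expect a small bias. It does not supply the missing assumption, because it is a planning value for a whole-group mean.

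Second, on mean squared error the one-arm version does at least as well. In 200,000 simulated trials per cell, restricted to trials in which both versions can be run, root mean squared error as written vs symmetric was:

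- p = 1/3: 3.40 vs 3.91 kg at d = 0; 3.58 vs 3.91 kg at d = 3; 3.87 vs 3.92 kg at d = 5
- p = 0.5: 3.94 vs 4.40 kg at d = 3; 4.34 vs 4.40 kg at d = 5

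These figures are right. They reflect the precision lost by shrinking an arm of five. That is an argument for declaring the choice and showing both versions; it does not justify an undeclared one-arm filter.

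Third, the phrase may simply be loose drafting for an exclusion meant in both arms. That is quite possible, and then one line settles it. Left alone, an analyst could follow the text literally.

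**Conclusion.** The concern holds. As written, item 2 compares a filtered arm with an unfiltered one, and its result is biased by p × d unless neuropathy is unrelated to untreated same-day grip change. For a d of about 1 kg the effect on type I error is negligible. The 0.090 figure needs half the patients to have neuropathy and a 5 kg untreated differential within hours. All sizes rest on assumed p and d, the plan's SD of 9 kg and r = 0.8, and equal spread within each neuropathy group.

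It should be fixed because the correction is easy and the present wording is wrong for a randomised comparison, but the stakes are low: one secondary analysis in a 15-patient pilot.

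**What to change.** Reword item 2 along these lines: *Repeat the primary test in patients whose nerve conduction studies show no neuropathy, applying the same exclusion to the lorcaserin and placebo groups.* In addition:

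- State the nerve conduction criterion for neuropathy. Reference 29, attached to this item, is listed as an article on lorcaserin for weight loss, so it does not supply one.
- Classify each patient without sight of grip results or allocation. The studies may be done at any time after randomisation, so grip results may already exist.
- Report the number excluded per arm. If fewer than two patients remain in either arm, describe the data without a test.
- If keeping all placebo patients is intended, state the assumption d = 0 and show that version beside the symmetric one.

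**Cost.** No new data, but less precision (SD of change 5.69 kg; half-width = t × 5.69 × √(1/n₁ + 1/n₂); power by noncentral t):

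| p | Patients left: symmetric vs as written | 95% half-width (kg) | Power at 9 kg |
|---|---|---|---|
| 0.2 | 8 and 4 vs 8 and 5 | 7.8 vs 7.1 | 64% vs 71% |
| 1/3 | about 7 and 3 vs 7 and 5 | 9.1 vs 7.4 | 52% vs 68% |

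Under the symmetric rule, the chance that an arm keeps fewer than two patients is 0.7% at p = 0.2, 4.6% at p = 1/3 and 20% at p = 0.5 (exact binomial). The result should be presented as descriptive.
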